4. STATISTICAL ANALYSES

4.1. General Considerations

4.1.1. General Methodology

Safety analysis set will be used for all study population analyses, safety analyses, and efficacy analyses.

Confidence intervals will use 95% confidence levels unless otherwise specified.

Unless otherwise specified, continuous data will be summarized using descriptive statistics: n, mean, standard deviation (std), median, minimum and maximum. Categorical data will be summarized as the number and percentage of participants in each category.

4.1.2. Baseline Definition

For all endpoints the baseline value will be the latest pre-dose assessment with a non-missing value, including those from unscheduled visits. For laboratory data, baseline will be the latest non-missing pre-dose value from local lab will be used.

Unless otherwise stated, if baseline data is missing no derivation will be performed and baseline will be set to missing.

4.2. Primary Endpoint(s) Analyses

The primary endpoint is DLT rate, AE's and SAE's. The analysis and reporting of AE's and SAE's are discussed in Section 4.5.

4.2.1. Definition of DLT

A DLT is defined as an AE that meets at least one of the criteria listed in protocol and is considered by the investigator to be clinically relevant and attributed (probably or possibly) to the study treatment during the 21-day DLT observation period.

4.2.2. Main analytical approach

A listing of adverse events recorded as dose-limiting toxicities during the determinative period will be provided. Additionally, a summary of the number of patients experiencing DLTs will also be provided.

4.2.3. Sensitivity analyses

No sensitivity analysis will be performed.

4.2.4. Additional estimands

No additional estimands are defined.

4.3. Secondary Endpoint(s) Analyses

4.3.1. Secondary endpoints

The secondary endpoints in part 1 are, Overall Response Rate (ORR) and Disease Control Rate (DCR).

4.3.1.1. Definition of Overall Response Rate (ORR) and Disease Control Rate (DCR)

ORR is defined as the percentage of participants with a best overall confirmed Complete Response (CR) or Partial Response (PR) at any time as per RECIST1.1

DCR is defined as the percentage of participants with best overall confirmed complete response, partial response or stable disease at any time as per RECIST1.1

Best overall response (BOR) will be derived on investigator assessments of overall response at each visit recorded from the start of treatment until the criteria for progression are met (considering any requirement for confirmation when needed), or the date of initiation of new anti-cancer therapy (Note: This excludes palliative radiotherapy), or death date, whichever is earliest, as assessed by the investigator per RECIST 1.1.

For RECIST 1.1,

To be assigned a status of confirmed CR/PR, a confirmatory disease assessment should be performed no less than 4 weeks (28 days) after the criteria for response are first met.

Responses of CR/PR that do not meet the requirements of confirmed CR/PR are still eligible to be considered SD if it has met the SD criteria.

For RECIST 1.1, to be assigned a status of SD, follow-up disease assessment(s) must have met the SD criteria at least once after the first dose at a minimum of 8 weeks (56 days) from baseline. If the minimum of 8 weeks (56 days) for SD is not met, the best overall response will depend on the subsequent assessments. For example, if an

assessment of PD follows the assessment of SD and SD does not meet the minimum 8-week requirement the best response will be PD. Alternatively, subjects lost to follow-up after an SD assessment not meeting the minimum time criteria will be considered not evaluable.

If NE (Not Evaluable) is recorded in between initial and confirmatory CR or PR then it can be disregarded to obtain the Best Response

A SD in between an initial PR and confirmation PR can also be disregarded to obtain the Best Response of PR (see below table)

4.3.1.2. Main analytical approach

ORR

The number and percentage of participants with the BOR in the following response categories will be summarized: CR, PR, iCR, iPR. The corresponding exact 95% CI for ORR and iORR will also be provided. Participants with unknown or missing responses will be treated as non-responders, i.e., these participants will be included in the denominator when calculating percentages of response. A figure displaying maximum reduction in tumor size and listing of subject level responses will be generated.

DCR

The number and percentage of participants with the BOR in the following response categories will be summarized: CR, PR, SD, iCR, iPR, iSD. The corresponding exact 95% CI for DCR and iDCR will also be provided. Participants with unknown or missing responses will be treated as non-responders, i.e., these participants will be included in the denominator when calculating percentages of response.

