1.2. Study Design

Overview of Study Design and Key Features	

Advanced NSCLC progressed on prior PD(L)1 & platinum chemo Stratify by squamous vs non-squamous Line of PD(L)1 therapy 1st vs. 2nd
 
Part 1: safety, PK/PD n = 10-15 per combination
 
Part 2: Survival
 
* Decision on each combination to proceed will be conditional on criteria from Section 5.1 and 10.5.1.1.
 
The two study populations (Part 1 and 2) are separate and distinct. Data from Part 1 and 2 will not be combined.
	
Between 10-20% of newly enrolled participants in subsequent substudies (depending upon the number of experimental arm trial) will be randomized to SoC once the initial 35 participants have been enrolled on control.
 
* Decision on each combination to proceed will be conditional on criteria from Section 5.1 and 10.5.1.1.
 
The two study populations (Part 1 and 2) are separate and distinct. Data from Part 1 and 2 will not be combined.

Design Features
 
 • A randomized, open-label, platform trial utilizing a master protocol • The study has 2 parts, i.e. part 1 and part 2. • Part 1 is a non-randomized part based on safety and pharmacokinetics/pharmacodynamics (PK/PD) evaluation. Part 2 is a randomized part, comparing the efficacy and safety of these novel regimens with SoC. • If the study passes part 1, then the participants will be recruited for part 2. • The final analysis for part 1 will be performed once all the participants complete 2 post baseline tumour assessments. • For part 2, interim analysis will be performed once 45 death events (18 in combination arm) are observed in the study. The primary analysis will be performed when 75 events are observed, and final analysis will be performed when 85 events are observed. • Arm 3 is getting terminated in part 1. 
Study intervention
 
 • The study will evaluate the safety and efficacy of feladilimab (ICOS agonist) in combination with ipilimumab. • There is no dose escalation in part 1, but the safety will be evaluated based on mTPI process • Combination study treatment will continue to be administered at the indicated schedule for a maximum duration of approximately 2 years or up to 35 treatment visits whichever comes first, or until disease progression as determined by iRECIST, death, unacceptable toxicity, or other protocol-defined criteria are met. 	

Overview of Study Design and Key Features						

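### Does taking both ORR/DCR and iORR/iDCR from one best overall response definition leave the response rates undefined?

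*SAP*

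**What the plan says.** Section 4.3.1.1 defines ORR and DCR under RECIST 1.1 only. It derives BOR from the investigator's visit assessments, starting with treatment and running "until the criteria for progression are met (considering any requirement for confirmation when needed), or the date of initiation of new anti-cancer therapy" (palliative radiotherapy does not count), "or death date, whichever is earliest, as assessed by the investigator per RECIST 1.1".

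The rules that follow carry the same label. For a confirmed CR or PR under RECIST 1.1, "a confirmatory disease assessment should be performed no less than 4 weeks (28 days) after the criteria for response are first met". For stable disease, the text reads "For RECIST 1.1, to be assigned a status of SD, follow-up disease assessment(s) must have met the SD criteria at least once", with a minimum of 56 days from baseline.

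Section 4.3.1.2 then widens the list of categories. For ORR: "The number and percentage of participants with the BOR in the following response categories will be summarized: CR, PR, iCR, iPR", followed by "The corresponding exact 95% CI for ORR and iORR will also be provided". For DCR: "CR, PR, SD, iCR, iPR, iSD. The corresponding exact 95% CI for DCR and iDCR will also be provided".

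Section 1.2 lets treatment run for about 2 years or 35 visits, "or until disease progression as determined by iRECIST, death, unacceptable toxicity, or other protocol-defined criteria are met". Assessments after a first RECIST 1.1 progression can therefore exist.

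**The concern.** Read quickly, Section 4.3.1 has one variable, one window and one label, yet four rates come out of it. The window ends at progression, and the bracket about confirmation does not say when confirmation of progression is needed. Two fixed stop points are conceivable, and neither suits both criteria.

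- **(a) Stop at first progression.** A response that appears afterwards cannot enter iORR or iDCR, so these add little or nothing to ORR and DCR.
- **(b) Stop at confirmed progression.** A response after a first progression could enter ORR and DCR, which are meant to be RECIST 1.1 rates.

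The visible text also gives no confirmation interval for iCR or iPR and no minimum duration for iSD. If this were a real fork, two programmers could report different preliminary efficacy from the same data. With at most 15 participants per dose level, one participant is visible in the rate.

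**Working it through.** The SAP gives no expected response rate, power or threshold for these endpoints, so there is no figure of its own to reproduce. Two questions can be checked: how much the stop point could matter, and which reading the text supports.

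**Inputs.** 10 to 15 participants per combination (Section 1.2); at most 15 per ipilimumab dose level (Section 5); exact 95% intervals (Section 4.3.1.2); 28 days to confirm a response and 56 days for stable disease (Section 4.3.1.1). *Assumptions:* iRECIST progression needs confirmation and RECIST 1.1 progression does not, which the visible SAP does not state; confirmed progression is modelled as two consecutive PD assessments; the visit sequences and counts are invented.

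**Step 1: does the stop point matter in principle?** Here later assessments are entered under the plain codes PR and SD, which is the worst case.

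| Sequence (study day) | Stop at first PD | Stop at confirmed PD |
|---|---|---|
| PD 63, PR 126, PR 168 (168 − 126 = 42 ≥ 28) | PD | PR |
| SD 63 (≥ 56), PD 126, PR 168, PR 210 (210 − 168 = 42 ≥ 28) | SD | PR |
| PD 63, PD 105 | PD | PD |
| PD 63, SD 105, SD 147 | PD | SD |

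BOR changes in three of the four sequences: ORR status in the first two, DCR status in the first and fourth. These show that the mechanism exists, not how often it occurs.

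**Step 2: size per participant.** 1/15 = 6.7 points; 1/10 = 10 points. Exact (Clopper-Pearson) limits for x of n are the 2.5% quantile of Beta(x, n − x + 1) and the 97.5% quantile of Beta(x + 1, n − x).

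| Rate | Without the extra participant | With the extra participant |
|---|---|---|
| Response, n = 15 | 2/15 = 13.3% (1.7 to 40.5) | 3/15 = 20.0% (4.3 to 48.1) |
| Response, n = 10 | 2/10 = 20.0% (2.5 to 55.6) | 3/10 = 30.0% (6.7 to 65.2) |
| Disease control, n = 15 | 6/15 = 40.0% (16.3 to 67.7) | 7/15 = 46.7% (21.3 to 73.4) |

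If 0 to 2 participants were affected at n = 15, the shift would be 0 to 2/15 = 13.3 points.

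**Step 3: which reading does the text support?**

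- Section 4.3.1.1 defines ORR and DCR by RECIST 1.1, and the BOR sentence ends with the same label. Reading (b) needs a programmer to set that label aside and the investigator to have recorded PR rather than iPR after progression.
- Section 4.3.1.2 keeps CR/PR/SD and iCR/iPR/iSD as distinct codes and asks for an interval for each rate. A response recorded as iPR does not count towards ORR.
- Asking for both ORR and iORR makes sense only if they can differ. In the n = 15 example, reading (a) gives 2/15 for both and reading (b) gives 3/15 for both. Letting the stop follow the criterion gives 2/15 and 3/15, which is the only outcome that serves the stated request.
- The bracket is conditional: confirmation is considered where it is required. Applied to two criteria, it gives first progression where none is required and confirmed progression where it is.

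The reading that reconciles all four points is the one an oncology statistician would program, and Section 7 cites the iRECIST guideline for the remaining detail.

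**The case for a change.** The best case for a change is that the favourable reading is inferred. The bracket does not name the criteria, its sentence closes with the RECIST 1.1 label, and iORR and iDCR have no definition in the visible Section 4.3.1. Even if the stop point is settled, confirmation of iCR/iPR and the minimum duration for iSD are not stated there. Termination does not remove the issue: Section 1 says this SAP governs the final outputs for arm 3, and the amendment dropped PK but kept these rates. Separate labels or a cross-reference would cost little.

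The description of the text stands: it is untidy, and two labels would read better. It does not show a wrong analysis. Part of the apparent gap lies where text cannot be seen. The exploratory objectives in Section 1.1 and all of Section 4.4 are redacted, the table announced at the end of Section 4.3.1.1 is not in the extracted text, and the protocol was not available. Section 4.3.1 names only ORR and DCR as secondary endpoints, and Section 4.3.2 says there are no others, so iRECIST rules could plausibly sit with the exploratory material. This cannot be verified, but nor can it be called an omission. The subject-level response listing in Section 4.3.1.2 would let a reader trace how an unusual case was classified.

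**Conclusion.** No change follows. The RECIST 1.1 rates are adequately defined, and contamination by responses after progression would require a strained reading together with unusual coding. For iORR and iDCR, what is left is a labelling gap that an analyst would fill from the cited guideline or from the protocol.

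The possible effect is 6.7 points per affected participant at n = 15 and 10 points at n = 10, with widely overlapping intervals. The number affected is unknown and may be zero. Section 2.1 applies no multiplicity adjustment in part 1, the SAP states no decision threshold for response, and the version history limits the outputs to supporting closure.

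This conclusion assumes that investigators record responses after progression under the iRECIST codes, and that analysts apply confirmation of progression only where the criterion calls for it.

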4.3.2. Supportive secondary endpoint(s)

No other secondary endpoints are defined.

4.4. Exploratory Endpoint Analyses

CCI

4.5. Safety Analyses

The safety analyses will be based on the Safety population.

4.5.1. Extent of Exposure

Extent of exposure to experimental arm will be summarized by Number of cycles, relative dose intensity and duration of exposure.

Relative dose intensity (RDI) is the percentage of the actual dose delivered relative to the intended dose. Relative dose intensity (RDI) is defined as (Actual cumulative dose

delivered up to treatment discontinuation)/(Planned cumulative dose up to treatment discontinuation)*100. The planned cumulative dose is the total dose that would be delivered, if there were no modification to dose or schedule. An RDI of 100% indicates that the drug was administered at the dose planned per protocol, without delay or reductions.

Treatment compliance is defined as (Actual cumulative dose/Scheduled cumulative dose)*100. The scheduled dose accounts for any dose reductions, for example, if a participant had a dose reduction from 75 mg/m² to 60 mg/m², then the scheduled dose is 60 mg/m².

Summary statistics will be produced for extent of exposure.

Duration of Exposure in weeks is defined as (treatment stop date – treatment start date + 1) divided by 7.

Dose reductions, infusion interruptions and incomplete infusions, and dose delays will be listed separately by dose.

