6.1.1. Participant Disposition

A summary of the number of subjects in each of the analysis sets described in Section 3 will be provided. Number of subjects based on the Safety will be summarized by country and site for each dose level.

A summary of subject status and reason for study withdrawal will be provided. This display will show the number and percentage of subjects who have completed the study or have withdrawn from the study, including primary and secondary (if any) reasons for study withdrawal. Reasons for study withdrawal will be presented in the order they are displayed in the eCRF (Electronic Case Report Form). Subjects who die for any reason during on-treatment period will be considered to have completed the study.

A summary of study treatment status will be provided. This display will show the number and percentage of subjects who discontinued study treatment and a summary of the primary reasons for discontinuation of study treatment. Reasons for study treatment discontinuation will be presented in the order they are displayed in the eCRF.

A listing of treatment discontinuation will be generated. The listing will include last dose date and primary reasons for study treatment discontinuation.

The number of subjects will be summarized by Country, Site ID and Investigator ID. This summary must be produced based on the safety population. The total column, summarizing subjects regardless of treatment, should always be included. Rows should be sorted alphabetically by country, then in numerical order by Site ID

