6.2.2. Study Period

6.2.2.1. Study Phases

Adverse events, serious adverse events, death and other safety domains will be assigned to the study phases defined below. Partial dates will be imputed into full dates, if applicable, for slotting data to the appropriate categories below. Flag variables (time in relation to study phase) indicating the study time periods will be added to the ADaM variable APHASE, and the treatment emergent AE flag will be created to ADAAE variable TRTEMFL.

Assessments and events will be classified according to the time of occurrence relative to Study Treatment Start Date.

Study Phase	Definition
Pre-Treatment	Date < Study Treatment Start Date
On-Treatment	Study Treatment Start Date \leq Date \leq Study Treatment Stop Date + 30 days
Post-Treatment	Date > Study Treatment Stop Date + 30 days

For parameters where time is not collected, Day 1 assessments are assumed to be taken prior to first dose and used as baseline.

Study Phase	Definition
Pre-Treatment	Date < Study Treatment Start Date
On-Treatment	Study Treatment Start Date \leq Date \leq Study Treatment Stop Date
Post-Treatment	Date > Study Treatment Stop Date

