		
 ○ If year of start date = year of study treatment start date, then 
 ▪ If stop date contains a full date and stop date is earlier than study treatment start date, then set start date = January 1. ▪ Else set start date = study treatment start date. • Else set start date = January 1.
	Missing end day	A '28/29/30/31' will be used for the day (dependent on the month and year)
	Missing end day and month	A '31' will be used for the day and 'Dec' will be used for the month.
	Completely missing start/end date	No imputation
New Anti-Cancer Therapy/ Radiotherapy/ Surgical Procedures for Efficacy Evaluation (e.g., response rate, time to event)		
 • Completely missing start dates will remain missing, with no imputation applied; • Partial start dates will be imputed using the following convention: 
 • If both month and day are missing, no imputation will be applied; • If only day is missing: 
 ○ If the month of partial date is the same as the month of last dosing date, minimum of (last dosing date + 1, last day of the month) will be used for the day; ○ If the month of partial date is the same as the month of last disease assessment and the last disease assessment is PD, minimum of (last date of disease assessment + 1, last day of the month) will be used for the day; ○ If both conditions above are met, the later date will be used for the day; ○ Otherwise, a '01' will be used for the day; • Completely or partial missing end dates will remain missing, with no imputation applied;
ECG		
 • Missing baseline values are assumed to have baseline value <450 for QTc

Trademarks

Trademarks of the GlaxoSmithKline Group of Companies	Trademarks not owned by the GlaxoSmithKline Group of Companies
NONE	SAS WinNonLin

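### Does an RDI of 100% really mean no delay, and does it matter that the treatment stop date for exposure is not defined?

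*SAP*

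**What the plan says.** Section 4.5.1 describes RDI first in words: "Relative dose intensity (RDI) is the percentage of the actual dose delivered relative to the intended dose". It then gives a ratio whose numerator and denominator both run to treatment discontinuation. The denominator is explained as follows: "The planned cumulative dose is the total dose that would be delivered, if there were no modification to dose or schedule". The interpretation offered is: "An RDI of 100% indicates that the drug was administered at the dose planned per protocol, without delay or reductions". Nothing is said about the cut-off date for planned dose, or about whole infusions versus a pro rata amount. Both agents are given every three weeks (dosing table, Section 1.2).

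The same section defines duration of exposure in weeks as the bracketed difference "treatment stop date – treatment start date + 1) divided by 7". The SAP uses the stop date again in Section 6.2.2.1 ("Study Treatment Stop Date + 30 days") and for the treatment-emergent flag in Section 6.2.2.3, without defining it. Elsewhere it speaks of the last dose: in Section 6.1.1 ("The listing will include last dose date and primary reasons for study treatment discontinuation") and in the Section 6.2.6 rule for partial dates of new anti-cancer therapy ("If the month of partial date is the same as the month of last dosing date").

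Section 4.5.1 also provides for listings: "Dose reductions, infusion interruptions and incomplete infusions, and dose delays will be listed separately by dose".

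**The concern.** An index said to equal 100% only when nothing was delayed should fall below 100% when something was. With infusions three weeks apart, a count of whole planned infusions moves only in steps of 21 days, so a shorter slippage can disappear. Two programmers could then produce different RDI values from the same data, and one set would not carry the meaning the SAP gives it.

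Duration raises a similar question. If the stop date is the last infusion, a participant with one infusion has 0.14 weeks of exposure; if it is the end of that cycle, 3.00 weeks. With few participants per dose level, such choices can move a summary visibly. As an assumed illustration, let 5 of 15 participants receive two full doses, the second 14 days late, and the other 10 stay on schedule. Mean RDI is 100% under whole-infusion counting and (10 × 100 + 5 × 75.0)/15 = 91.7% under pro rata counting.

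**Working it through.** **Inputs.** Dosing interval 21 days (Section 1.2). RDI and duration as defined in Section 4.5.1. Let k be the number of full-dose infusions and D the net delay in days, so that the last infusion falls 21(k − 1) + D days after the first. The values of k and D are illustrative; the SAP gives none.

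**Three ways to count planned dose.**

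- (a) Whole infusions due by the last infusion: planned = k + floor(D/21), RDI = 100k/(k + floor(D/21)).
- (b) Pro rata to 21 days after the last infusion: RDI = 100 × 21k/(21k + D).
- (c) Whole infusions due by 20 days after the last infusion: planned = floor((21(k − 1) + D + 20)/21) + 1.

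**The SAP's own figure.** With D = 0, all three give 100%, so full-dose treatment on schedule scores as stated. The question is whether 100% excludes a delay.

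| k | D (days) | (a) | (b) | (c) |
|---|---|---|---|---|
| 2 | 1 | 100% | 97.7% | 66.7% |
| 2 | 14 | 100% | 75.0% | 66.7% |
| 2 | 20 | 100% | 67.7% | 66.7% |
| 2 | 21 | 66.7% | 66.7% | 66.7% |
| 4 | 1 | 100% | 98.8% | 80.0% |
| 4 | 14 | 100% | 85.7% | 80.0% |
| 4 | 20 | 100% | 80.8% | 80.0% |
| 4 | 21 | 80.0% | 80.0% | 80.0% |

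Under (a), net delays of 1 to 20 days are hidden for any k. Under (b) and (c), none is.

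**How far (a) follows from the text.** Section 4.5.1 runs the ratio to discontinuation, not to the last infusion. If discontinuation falls g days after the last infusion and whole infusions are counted to that date, planned = k + floor((D + g)/21). With full doses, RDI stays at 100% only when D + g < 21:

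- g = 0: delays of 1 to 20 days are hidden;
- g = 14: delays of 1 to 6 days are hidden;
- g = 20: none is hidden.

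The 1-to-20-day range is therefore the worst case. It requires discontinuation to be dated on the day of the last infusion.

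**Would a tighter formula make the sentence exact?** Take full doses on Days 1, 25 and 43. The second is 3 days late (due Day 22) and the third is on its original date. The pro rata denominator is (42 + 21)/21 = 3 cycles, so RDI = 3/3 = 100%. Rules (a) and (c) also count 3 planned infusions. All three see net delay only; a delay that is later caught up shows only in the listing.

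**Duration, on-time infusions.**

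| k | Stop date = last infusion | Stop date = end of cycle |
|---|---|---|
| 1 | 1/7 = 0.14 weeks | 21/7 = 3.00 weeks |
| 2 | 22/7 = 3.14 weeks | 42/7 = 6.00 weeks |
| 4 | 64/7 = 9.14 weeks | 84/7 = 12.00 weeks |

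The difference is 20 days for every k. It is a constant shift between two conventions and does not depend on how treatment went.

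**The case for a change.** The strongest case for a change has three parts.

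First, the SAP does not rule out counting (a), and under (a) the sentence about 100% is untrue. That stands as a statement about one possible reading. But the sentence itself says that RDI should respond to delay, and planned dose is defined by an unmodified schedule. A programmer choosing between rules has a clear steer away from the one that contradicts the section.

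Second, the stop date also anchors the 30-day on-treatment and treatment-emergent windows, and adverse events are a primary endpoint. A 20-day shift would move that boundary. This is the weightiest part. However, nothing in the SAP suggests an end-of-cycle stop date. Its references to the last dose are compatible with reading the stop date as the date of last dose, the natural reading for infusions, and that gives a settled window. The protocol or the sponsor's data standards may also define the term; neither is at hand.

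Third, dose modifications are among the primary endpoints in Section 1.1, and RDI is the exposure summary that combines delays with reductions. True, but number of cycles is summarised as well, and reductions, interruptions and delays are listed. With at most 15 participants per dose level (Section 5), a listing can be read in full and tells more than a mean RDI.

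**Conclusion.** The gap is real but minor: the SAP states neither a cut-off date nor a counting rule for planned dose, and does not define the stop date. No number in it is wrong. In the worst case, net delays of up to 20 days are hidden, which for a participant with two full doses means 100% instead of 67.7%. That requires a counting rule at odds with the section's stated meaning and discontinuation dated at the last infusion. The duration difference is a fixed 20 days between two legitimate conventions, and a table footnote can say which was used.

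No change to the plan follows. Analysts can fill the gap with a rule that matches the stated interpretation. A more elaborate formula based on first and last infusion dates would still miss delays that are caught up, whereas the planned listing shows them. Section 1.2 says the arm is being terminated in Part 1, the version history says outputs were cut back to support closure, and no test or decision uses RDI or duration.

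This rests on two assumptions: that the stop date is read as the date of last dose for the safety windows, and that the programmed RDI rule is made visible with the output.
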